## 106 2.0 Background/Scientific Rationale

107 Asthma is a highly prevalent chronic disease that disproportionately impacts African  
108 American (AA) women. AA women have poorer asthma-related quality of life and higher  
109 rates of asthma exacerbations, healthcare utilization and mortality compared to  
110 Caucasian women. Further, AA women are less physically active than any other  
111 subgroup of adults, which may help explain the asthma health disparities, found  
112 between AA and Caucasian women. Physical inactivity among individuals with asthma  
113 is associated with poor asthma control and respiratory function, greater health care  
114 utilization, and poorer quality of life. Given the connection between poor asthma  
115 outcomes and physical inactivity, addressing physical activity (PA) among sedentary AA  
116 women with asthma is imperative. Physical activity demonstrated improvement in  
117 asthma outcomes specifically asthma control, quality of life and healthcare utilization.  
118 Despite these benefits, fewer than 25% of AA women with asthma engage in regular  
119 physical activity. The **ACTION intervention: physicAl aCtivity In minOrity womeN  
120 with asthma** is a 8-month community-based walking intervention refined to be  
121 applicable for sedentary AA women with asthma.  
122

123 This project will obtain and incorporate stakeholder input on the barriers and facilitators  
124 to engaging in physical activity with asthma to a validated community-based walking  
125 intervention. Once modified, we will pre-pilot the intervention in 10 participants, refine  
126 further in response to participant feedback and then test the feasibility, acceptability and  
127 estimate the efficacy of the intervention in a randomized controlled pilot of 80  
128 participants within a pragmatic community setting convenient for sedentary AA women.  
129

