## 131 3.0 Objectives/Aims

132 The proposed study has 5 aims involving a total of 135 sedentary AA women with  
133 asthma.  
134

135 **NOTE:** Aims 1 and 2 have been IRB approved and completed. Only data analysis of  
136 these 2 aims are still occurring. At this time, I am requesting approval for Aim 3 which  
137 entails pilot testing the intervention to assess the feasibility, acceptability and to  
138 estimate the efficacy of the ACTION intervention.  
139

140 **Aim 1:** Use stakeholder input to modify a validated walking intervention for sedentary  
141 AA women with asthma.

[figure not shown]
142 **Aim 1a:** Conduct focus groups in 30 sedentary AA women with asthma to assess PA  
143 barriers and facilitators.  
144

145 **Aim 1b:** Adapt a validated walking intervention that addresses the barriers and  
146 facilitators to PA unique to sedentary AA women with asthma obtained from Aim 1A.  
147  
148

149 **Aim 2:** Pre-pilot test ACTION (physicAl aCtivity In minOrity womeN with asthma)  
150 intervention in up to 10 sedentary AA women with asthma to refine the recruitment  
151

152 materials, approach, design, and intervention content.

[figure not shown]
Figure 1. Study Design for ACTION Pre-pilot

153  
154  
155  
157  
158  
159  
160

**Aim 3:** Pilot test ACTION intervention in 80 sedentary AA women with asthma to assess acceptability, feasibility and estimate the efficacy to appropriately power a subsequent efficacy trial.

Figure 2. Study Design for Aim 3 (ACTION RCT Pilot)

161  
162  
163  
164  
165  
166  
167  
168  
169  
170  
171  
172  
173  
174  
175  
176

**Aim 4:** Modify and refine the video component of the intervention to address the asthma-specific barriers to walking in AA women with asthma.

**Aim 4a:** Conduct a focus group with an Asthma Advisory Council (AAC) that includes up to 15 AA women with asthma, to assess the appropriateness of the proposed asthma content, language and setting used in the videos.

**Aim 4b:** Adapt the video component of the intervention using an iterative approach to include appropriate asthma content, language and setting.

**Aim 5:** Assess the acceptability of the revised videos by the AAC using a mixed methods approach (qualitative and quantitative data).

**Aim 6:** Disseminate research findings and next steps to women that participated in Aims 1-3.

177 **4.0 Eligibility/Inclusion and Exclusion Criteria (for Aims 1, 2 and 3)**

178

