### 569 570 **3 Data Collection Visits: Baseline (week 0/Visit 1), post adoption phase (week** 571 **24/Visit 7a/b) and post maintenance phase (week 36/Visit 9) in all participants** 572 **(See appendix 8 for measures)**

573 At the data collection visits, the following procedures will take place at the Clinical  
574 Research Center at UIC or Chicago Park District location:

- 575 1. Secure informed consent (1st visit only).
- 576 2. Complete a brief demographic form.
- 577 3. Spirometry performed according to American Thoracic Society guidelines.  
578 Participants will be asked to wear nose clips and to take a deep breath in and  
579 blow their breath out as fast as they can into the spirometer. We will perform  
580 repeated measurements (3 to 8 times) to ensure accuracy of results.
- 581 4. Height and Weight
- 582 5. Incremental Shuttle Walk Test (ISWT) performed according to American  
583 Thoracic Society guidelines
- 584 6. Physical activity questionnaires

- 585 7. Asthma Safety Measures  
586 8. Asthma Control Questionnaire (ACQ)  
587 9. Asthma-related quality of life questionnaire (AQLQ)  
588 10. Adult Asthma Adherence Questionnaire (AAAQ)  
589 11. PROMIS measures (Global Health, social roles satisfaction, mood, sleep)  
590 12. Active Where Questionnaire  
591 13. Self-efficacy for walking scale  
592 14. Social support for exercise survey  
593 15. Outcome expectation scale for exercise  
594 16. Sleep Apnea Scale of the Sleep Disorders Questionnaire  
595 17. Pittsburgh Sleep Quality Instrument  
596 18. Neighborhood safety and social cohesion questionnaire  
597 19. Study randomization (1st visit only)  
598 20. Schedule asthma and physical activity (PA) education session with participant  
599 (1st visit only)  
600

601 Key research personnel will obtain consent in a private room in the Clinical  
602 Research Center. After consent is obtained, the other study procedures will be  
603 completed.  
604

605 This visit will last approximately 2 hours and upon completion the participant will  
606 receive \$35 cash or gift card. Patients will be offered light snacks/refreshments  
607 at this visit and given a visit summary sheet with their blood pressure, heart rate,  
608 weight, height, oxygen level, date of next study visit and a copy of spirometry  
609 results if desired.  
610

611 Participants will then be provided the following equipment at these data collection  
612 visits:

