749 repeated measurements (3 to 8 times) to ensure accuracy of results.
- 750 2. Weight
- 751 3. Incremental Shuttle Walk Test (ISWT) performed according to American  
752 Thoracic Society guidelines
- 753 4. Accelerometer distribution
- 754 5. Summative evaluation (visit 7 only; Appendix 10)

755

756 If a participant is not able to attend this session, we will contact the patient to scheduled  
757 an in person data collection visit at UI Health/UIC where the above procedures (#1-3)  
758 will be completed.

759

760 During or after Visit 7a is complete, participants will complete REDCap paper surveys (  
761 in person) or will be sent a link (email or text) to complete the following REDCap  
762 surveys electronically:

- 763 1. Physical activity questionnaires
- 764 2. Asthma Safety Measures
- 765 3. Asthma Control Questionnaire (ACQ)
- 766 4. Asthma-related quality of life questionnaire (AQLQ)
- 767 5. Adult Asthma Adherence Questionnaire (AAAQ)
- 768 6. PROMIS measures (Global Health, social roles satisfaction, mood, sleep)
- 769 7. Active Where Questionnaire
- 770 8. Self-efficacy for walking scale
- 771 9. Social support for exercise survey
- 772 10. Outcome expectation scale for exercise
- 773 11. Sleep Apnea Scale of the Sleep Disorders Questionnaire
- 774 12. Pittsburgh Sleep Quality Instrument

775 Key research personnel will send a reminder text, call and/or email (based on patient  
776 preference) up to 3 times the prior week to the group session stating “ACTION Asthma  
777 group will meet at X time and X place.”

778

779 Reminder messages will also be sent via phone, text or email (based on participant  
780 preference) up to 3 times per week to help them attain their weekly step goal (See  
781 Appendix 11 for sample text messaging).

782

783 An interventionist and/or [name] will attend the group sessions. Each group will  
784 last approximately 2 hours and may be audio-recorded to assess for intervention fidelity.  
785 If a participant declines audio-recording the session, then the session will not be  
786 recorded. The PI or co-investigator may then observe a group session intermittently to  
787 assess for intervention fidelity. If the session is recorded, the PI will review portions of  
788 the session. The sessions will be deleted once the pilot is complete. These audio  
789 recordings will not be transcribed. Patients will receive light snacks/refreshments at  
790 each session.

791

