792 If any of the group visits 3-7 are missed, the woman is asked to arrive 15 minutes early  
793 for the next meeting to receive an update. Her report will be emailed/phones/texted to her  
794 depending on her preference.

795

796 If a woman has missed several group visits and we have been unable to contact her, we  
797 will mail her a letter indicating to call us.

798

799 **Visit 7b: 24 week data collection (Enhanced Usual Care only)**

800 At Visit 7b the following procedures will take place at the Clinical Research Center at  
801 UIC:

- 802 1. Spirometry performed according to American Thoracic Society guidelines.  
803 Participants will be asked to wear nose clips and to take a deep breath in and  
804 blow their breath out as fast as they can into the spirometer. We will perform  
805 repeated measurements (3 to 8 times) to ensure accuracy of results.
- 806 2. Weight
- 807 3. Incremental Shuttle Walk Test (ISWT) performed according to American  
808 Thoracic Society guidelines
- 809 4. Accelerometer distribution
- 810 5. Physical activity questionnaires
- 811 6. Asthma Safety Measures
- 812 7. Asthma Control Questionnaire (ACQ)
- 813 8. Asthma-related quality of life questionnaire (AQLQ)
- 814 9. Adult Asthma Adherence Questionnaire (AAAQ)
- 815 10. PROMIS measures (Global Health, social roles satisfaction, mood, sleep)
- 816 11. Active Where Questionnaire
- 817 12. Self-efficacy for walking scale
- 818 13. Social support for exercise survey
- 819 14. Outcome expectation scale for exercise
- 820 15. Sleep Apnea Scale of the Sleep Disorders Questionnaire
- 821 16. Pittsburgh Sleep Quality Instrument

822

823 This visit will last approximately 2 hours and upon completion the participant will receive  
824 \$35 cash or gift card.

825

826 Participants will be given a postage paid envelope and be asked to mail the  
827 accelerometer back to study team after wearing it for 1 week. Reminder  
828 calls/texts/emails will be sent if we have not received the accelerometer within 2 weeks  
829 of completion of visit 7. If needed, a central location for drop-off of the accelerometer  
830 may be arranged with the participant.

831

832 **Maintenance Phase:** During the maintenance phase, participants will continue to  
833 receive reminder text messages to help them attain their weekly step goal no more than  
834 once a week.

835

836 **Visit 8: Post-maintenance booster session and data collection (12 weeks after**  

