837 **Visit 7) Booster session will only be for intervention group.**

838

839 At visit 8 booster session the following procedures will occur:

- 840 1. Attend a 2 hour group session at the Chicago Park District or at UI  
841 Health/UIC. At the group session, participants will review successes attained  
842 and barriers, lapses, and relapses encountered.
- 843 2. Participants will be asked to complete a session evaluation form. (Appendix 9).
- 844 3. Participants will be given \$5 cash to assist with travel expenses incurred for  
845 the group visit.

846

847 An interventionist and/or [name] will attend the group session. The group will last  
848 approximately 2 hours and may be digitally recorded to assess for intervention fidelity. If  
849 a participant declines audio-recording the session, then the session will not be  
850 recorded. The PI or co-investigator may then observe a group session intermittently to  
851 assess for intervention fidelity. If the session is recorded, the PI will review portions of  
852 the session. The session will be deleted once the pilot is complete. These audio  
853 recordings will not be transcribed. Patients will receive light snacks/refreshments at the  
854 session.

855

856 **Post-maintenance data collection (all participants)**

857 The following procedures will take place at the Chicago Park District (intervention  
858 group) or Clinical Research Center at UIC (enhanced usual care):

- 859 1. Spirometry performed according to American Thoracic Society guidelines.  
860 Participants will be asked to wear nose clips and to take a deep breath in and  
861 blow their breath out as fast as they can into the spirometer. We will perform  
862 repeated measurements (3 to 8 times) to ensure accuracy of results.

- 863 2. Weight  
864 3. Incremental Shuttle Walk Test (ISWT) performed according to American  
865 Thoracic Society guidelines  
866 4. Distribution of accelerometer  
867  
868

869 The following questionnaires will be completed by REDCap survey:

- 870 1. Physical activity questionnaires  
871 2. Asthma Safety Measures  
872 3. Asthma Control Questionnaire (ACQ)  
873 4. Asthma-related quality of life questionnaire (AQLQ)  
874 5. Adult Asthma Adherence Questionnaire (AAAQ)  
875 6. PROMIS measures (Global Health, social roles satisfaction, mood, sleep)  
876 7. Active Where Questionnaire  
877 8. Self-efficacy for walking scale  
878 9. Social support for exercise survey  

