## APPENDICES

*Appendix 1: Asthma Control Questionnaire (ACQ)*

*Appendix 2: Asthma Control Test (ACT)*

*Appendix 3: EASY Questionnaire*

*Appendix 4: Asthma Algorithm*

*Appendix 5: Basic Demographics Information*

*Appendix 6: Focus Group Guide/Questions*

*Appendix 7: Table of study procedures (pre-pilot 7a and pilot 7b)*

*Appendix 8: Survey measures*

*Appendix 9: Evaluation of group session*

*Appendix 10: Summative evaluation of intervention*

*Appendix 11: Text message content*

*Appendix 12: Focus group guide for adapting intervention tools*

*Appendix 13: Video Acceptability measure*

*Appendix 14: Sample dissemination newsletters*

*Appendix 15: Cover letter/email to accompany dissemination newsletter*

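### The pilot's only overall evaluation of ACTION is taken at week 24, before the 12-week maintenance phase and the booster

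*Combined protocol and SAP*

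**What the plan says.** Section 3.0 sets the aim: "Pilot test ACTION intervention in 80 sedentary AA women with asthma to assess acceptability, feasibility and estimate the efficacy". Section 2.0 says that ACTION "is a 8-month community-based walking intervention refined to be" suitable for this population, and Section 6.0 (Aim 3, Group sessions) divides it into adoption and maintenance phases.

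The relevant forms and times in Section 6.0, Aim 3, are:

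- **Last adoption session (Visit 7a, week 24).** Item 5 of the procedure list is "Summative evaluation (visit 7 only; Appendix 10". The appendix list gives the title of Appendix 10 as "Summative evaluation of intervention".
- **Maintenance phase.** Participants "receive reminder text messages to help them attain their weekly step goal no more than" once a week. No group session is scheduled until the booster.
- **Booster.** The heading is "Visit 8: Post-maintenance booster session and data collection (12 weeks after" Visit 7. Its list includes the session form: "Participants will be asked to complete a session evaluation form. (Appendix 9". The same form is used at the education session and at each adoption session.
- **Week-36 data collection.** The heading of the data collection section places it after maintenance, "and post maintenance phase (week 36/Visit 9) in all participants". The REDCap list for that time has twelve entries, and Appendix 10 is not one of them.
- **Missed Visit 7a.** The make-up visit covers procedures 1 to 3 of the Visit 7a list.

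**The concern.** The rating that looks like the overall verdict on the programme is collected when a third of the programme has still to happen. The remaining third also differs in kind. Support falls from group sessions every 4 weeks and up to three messages a week to at most one message a week, with a single booster at the end. Women may rate this lighter-contact phase differently. That is a reasonable expectation, although the protocol does not claim it.

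Aim 3 exists to prepare a later efficacy trial. Its designers will have to decide whether to keep, strengthen or drop the maintenance component, and under the present schedule they would have no overall participant rating that covers it. A summary reported simply as the acceptability of ACTION would in fact describe the adoption phase, and only among women who attended its last session.

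**Working it through.** The plan states no acceptability figure or threshold for Aim 3, so there is nothing to reproduce. The check compares the timeline with the lists of instruments.

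**1. Does the 8-month description include maintenance?** Week 36 is 36 × 7 = 252 days, and 252/365 × 12 = 8.3 months. Week 24 is 24 × 7 = 168 days, and 168/365 × 12 = 5.5 months. Only the 36-week count matches 8 months, so the intervention as described includes the maintenance phase.

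**2. How much follows the summative form?**

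- Time: 36 − 24 = 12 weeks, and 12/36 = 33%. The booster heading agrees, since it sets that visit 12 weeks after Visit 7.
- Intervention-only group sessions: 5 adoption + 1 booster = 6, so 1/6 = 17% follow the form.
- All intervention-arm group contacts, including the education session: 1 + 5 + 1 = 7, so 1/7 = 14% follow it.

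**3. Is an overall rating collected later by another route?**

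| Source after week 24 | What the text provides |
|---|---|
| Booster list | Session form (Appendix 9), titled as an evaluation of a group session |
| Booster discussion | Review of progress and setbacks; any recording is for fidelity, is not transcribed and is deleted |
| Week-36 REDCap list | Twelve questionnaires, without Appendix 10 |
| Attendance | No group session between Visits 7 and 8, so it says nothing about that interval |
| Retention and Fitbit data | Engagement, not how women rated the reduced contact |

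The session form at the booster is therefore the only later source that records participants' ratings in a form that can be analysed. Section 9.0 confirms that session evaluations count as Aim 3 data.

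**4. Who is scheduled for the summative form at week 24?** The Visit 7a list is (1) spirometry, (2) weight, (3) shuttle walk, (4) accelerometer distribution, (5) summative evaluation. The make-up visit covers 1 to 3, so item 5 is left out. The twelve surveys completed during or after Visit 7a do not include Appendix 10 either. A woman who misses that session therefore has no scheduled overall evaluation at any time. If absence goes with a less favourable view, which is an assumption, the collected ratings lean upwards.

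The allocation ratio is not stated, and neither is expected attendance at Visit 7a. The gap is therefore given in weeks and sessions, not in numbers of women.

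**The case against.** The strongest reply is that the plan never says acceptability in Aim 3 is measured by Appendix 10. That is correct. Aim 3 names no acceptability instrument. The one statement tying acceptability to a summative evaluation, in Section 9.0, concerns the Aim 5 videos. A reader might infer that Aim 3 cannot answer its acceptability objective, or that no acceptability data exist after week 24. The documents support neither reading. Session forms are collected at all seven group contacts, including the booster after maintenance, and attendance and retention are reviewed throughout.

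The appendices are also listed by title only. Appendix 9 as used at the booster may ask about the preceding weeks, and the procedures table in Appendix 7 may add to the schedule. This limits the finding to what the protocol text shows.

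A reader might also see a departure from the pre-pilot, where the same form came at the final visit. That comparison is weak. The pre-pilot had no maintenance phase, and in both studies the form falls at the last regular group session. Rating the programme at the end of its intensive phase is a defensible choice for a pilot with no formal sample-size basis. The 33% is calendar time; counted by group contacts, the share after Visit 7 is 14%.

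What remains is narrower. The only form titled as an evaluation of the whole intervention comes before the maintenance phase, no other listed instrument is dedicated to an overall rating of that phase, and women absent from Visit 7a are not scheduled for the form.

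**Conclusion.** The point holds as a timing and coverage gap. The single overall evaluation falls at week 24, leaving 12 of 36 weeks (33%) and the booster without a dedicated overall rating in the protocol text. Women who miss Visit 7a have none scheduled. Partial evidence after week 24 does exist through the booster's session form, so the acceptability objective is weakened for the full programme, not defeated.

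The conclusion assumes that Appendices 9 and 10 do what their titles say, and that Appendix 7 does not schedule Appendix 10 again at week 36. If the booster version of Appendix 9 already asks for a rating of the maintenance texts, the gap narrows to women who do not attend the booster. The correction is cheap and worth making.

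**What to change.** - In the Visit 7a list, change the timing of Appendix 10 from Visit 7 alone to Visit 7 and week 36. State the time as week 36, because the protocol calls that collection Visit 9 in one place and treats it under Visit 8 in another. Those labels should be reconciled.
- Add Appendix 10 to the week-36 REDCap list for every intervention-arm woman, whether or not she attended Visit 7a or the booster. For booster attenders, send it after that session.
- If the form has no item on the maintenance texts and the booster, add a short one and leave the existing items unchanged, so that the week-24 and week-36 answers can be compared.
- Report the week-24 rating as adoption-phase acceptability and the week-36 rating as full-programme acceptability, each with the number of women who responded.

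The cost is a few minutes of extra questionnaire time per woman and possibly a small adaptation of the form. No new visit is needed, and treatment and sample size are unchanged.

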613 Actigraph accelerometer: This will be given to participants to assess their baseline  
614 and post-intervention daily number of steps. Participants will be verbally instructed  
615 to wear it attached to their wrist at all times while awake. The Actigraph  
616 accelerometer (Figure 3) is a research accelerometer (1.8 inches at its largest  
617 dimension, weight 19 grams). This will be returned within 2 weeks of the data  
618 collection visit. The accelerometers can be returned either in person at the asthma  
619 and PA session, in a postage paid envelope or the participant and the research  
620 assistant will find a mutually agreeable place to pick up the accelerometer from the  
621 participant. The participant will not incur any charges if the accelerometer is lost or  
622 stolen. The data from the accelerometers will be downloaded to Actigraph software  
623 (ActiLife 6.13.3) when the accelerometers are returned. Only study ID will be used

624 in the actigraph software. No identifiable information will be maintained in the  
625 Actigraph software.

626  
627 Participants are typically asked to wear the accelerometer for 7 days (does not  
628 have to be consecutive). However, valid baseline measurement of activity can be  
629 obtained with an average of 10 hours per day for 4 days. This is the minimum  
630 amount of accelerometer data required to continue participation in the intervention.  
631 If the participant does not wear the accelerometer for sufficient time to provide valid  
632 baseline measure (ie. an average of 10 hours per day for 4 days), they will be  
633 offered a second opportunity to wear the accelerometer. If the participant declines  
634 or is unable to wear the accelerometer again within 3 weeks of returning the  
635 accelerometer, then the participant will be withdrawn from the study.

636  
637 **Enhanced Usual Care Group (home-based walking program):** The comparison  
638 group will be instructed to achieve a static goal of 10,000 steps per day. The US  
639 Surgeon General recommends accumulating 30 minutes of activity most days of the  
640 week. Assuming that an individual gets 6,000 steps from their other daily activities, 30  
641 minutes of walking can help one achieve a goal of approximately 10,000 steps per day.

642  
643 Participants will be given a Fitbit Charge HR® which will measure their daily steps (see  

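### The make-up visit for a missed Visit 7a names three of five procedures, leaving the summative evaluation unassigned and accelerometer distribution unclear

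*Combined protocol and SAP*

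**What the plan says.** All references are to the combined protocol and SAP, section 6.0, Aim 3 (Pilot), unless stated.

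- **Visit 7a list.** The last adoption-phase group session carries five numbered procedures: (1) spirometry, (2) weight, (3) shuttle walk test, (4) accelerometer distribution, (5) "Summative evaluation (visit 7 only; Appendix 10").
- **Make-up for Visit 7a.** A woman unable to attend is to be scheduled for "an in person data collection visit at UI Health/UIC where the above procedures (#1-3") are completed.
- **General rule for data collection visits.** The heading covers baseline, week "24/Visit 7a/b) and post maintenance phase (week 36/Visit 9) in all participants". The text beneath it says "Participants will then be provided the following equipment at these data collection" visits, and names the Actigraph, whose purpose is to measure baseline "and post-intervention daily number of steps".
- **Missed group sessions.** "If any of the group visits 3-7 are missed, the woman is asked to arrive 15 minutes early" for the next meeting, to be given an update. Separate text under the asthma and physical activity education session offers make-up sessions in person or by video.
- **Next meeting after Visit 7.** "Visit 8: Post-maintenance booster session and data collection (12 weeks after" Visit 7).
- **Comparison arm at week 24.** "Visit 7b: 24 week data collection (Enhanced Usual Care only") includes accelerometer distribution.

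Section 3.0 gives Aim 3's purpose: to assess acceptability and feasibility, and to estimate efficacy so that a later trial can be powered.

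**The concern.** Five items are numbered, and the sentence that follows carries only the first three to the make-up visit. Two kinds of data that serve Aim 3 are affected.

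The summative evaluation is the only scheduled overall assessment of the intervention by its users. If it is not collected at the make-up visit, acceptability is described only by women who came to the last session. Women who could not come to that session might hold a different view of the programme, and they are the ones left out.

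The accelerometer gives the research-grade step count at week 24. If the device is not handed out, a woman who is on site at the right time leaves without it, and her week-24 Actigraph steps are missing because of the visit instruction and not because of anything she did.

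**Working it through.** The plan states no figure on this point, so the check is a comparison of lists and a count.

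**Step 1: the five procedures against the make-up sentence**

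| Visit 7a procedure | Named for make-up visit | Provided for elsewhere if Visit 7a is missed |
|---|---|---|
| 1 Spirometry | yes | not needed |
| 2 Weight | yes | not needed |
| 3 Shuttle walk test | yes | not needed |
| 4 Accelerometer distribution | no | possibly, by the general equipment rule |
| 5 Summative evaluation | no | nowhere found |

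Listed 5, named 3, left out 5 − 3 = 2.

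**Step 2: does other Aim 3 text pick up the summative evaluation?**
- The REDCap surveys completed during or after Visit 7a comprise 12 instruments, and the summative evaluation is not one of them.
- The rule for missed visits 3-7 offers an update at the next meeting. After Visit 7 that meeting is the booster, 12 weeks later. Its list has the session evaluation form (Appendix 9) but not the summative evaluation (Appendix 10).
- The make-up text under the education session has unclear scope and does not mention the evaluation.
- The item itself is restricted to Visit 7.

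Scheduled summative evaluations: 1. Without item 5 at the make-up visit: 1 − 1 = 0.

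**Step 3: does other text pick up the accelerometer?**
- The general rule gives the Actigraph at the data collection visits, including week 24, in all participants. The make-up visit is itself described as a data collection visit, so the rule can be read to cover it.
- The specific instruction stops at item 3. Staff following it literally would not hand out the device. The postage-paid envelopes are for return; no text describes sending a device out.

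Scheduled Actigraph readings: weeks 0, 24 and 36 = 3.
- Literal reading of the make-up sentence: 3 − 1 = 2.
- General equipment rule applied: 3.

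**Step 4: how many women?**

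The documents give neither an allocation ratio nor an expected rate of missing Visit 7a, so this cannot be determined. For scale only, assume equal allocation of the 80 women: 80 / 2 = 40 in the intervention group, and each woman affected is 1 / 40 = 2.5% of it. If 10% to 30% missed Visit 7a and came to the make-up visit (also assumed), that would be 0.10 × 40 = 4 to 0.30 × 40 = 12 women. The point does not depend on these assumptions.

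**The case against.** The strongest reply concerns the accelerometer. The make-up visit replaces Visit 7a and is called a data collection visit, so the general equipment rule reasonably applies. The sentence does not say that nothing else may be done. The visit lists are also loose. The general list includes the demographic form, height and the neighborhood questionnaire without limiting them to the first visit, yet the Visit 7a and 7b lists omit them. Omission from a list is therefore weak evidence of intent, and a slip in wording is more likely than a design decision. This stands: the loss of week-24 Actigraph steps is conditional, and a reader who infers a flat contradiction or a certain loss goes further than the text allows.

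A reader might also infer an imbalance between arms, because a make-up is written for Visit 7a and none for Visit 7b. The documents do not support that. Visit 7a is tied to a group session and needs a written substitute. Visit 7b is a data collection visit at the research center, is not described as a group session, and nothing bars rescheduling it.

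The stakes are limited as well. Section 11.0 has no sample size calculation for Aim 3, and neither section 9.0 nor section 11.0 specifies a week-24 step analysis. Fitbit steps, questionnaires, session evaluation forms and week-36 accelerometry remain. Appendix 7b, the pilot procedures table, might assign both items, but it is only listed and its content is not in the document.

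None of this supplies a route for the summative evaluation in the available text.

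**Conclusion.** The point holds, at minor severity. As written, a woman seen at the make-up visit has 0 of 1 scheduled summative evaluations, so the overall acceptability data would come only from women who attended the last session. For the accelerometer, the make-up sentence and the general equipment rule do not match and need to be reconciled. She has 2 of 3 scheduled Actigraph readings if the former is followed literally, and 3 of 3 if the latter governs.

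The number of women affected and the direction of any bias cannot be determined, and no shift in mean steps is claimed. The conclusion about the summative evaluation assumes that Appendix 7b does not assign it to the make-up visit.

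**What to change.** In the make-up sentence under the Adoption phase, change the range from #1-3 to #1-5. This aligns it with the general equipment rule and gives the summative evaluation a place.

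If the evaluation is not meant to be done in person at that visit, change the range to #1-4 and add the summative evaluation to the Visit 7a REDCap surveys. In that case, state that those surveys also go to women seen at the make-up visit.

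Check either change against the pilot procedures table in Appendix 7b so that the two agree.

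The cost is a very small text edit, a few more accelerometers handed out (with the return arrangements already in use) and one more form per woman seen at a make-up visit.
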